## 2.1. Primary Objectives

For this feasibility study we will assess the safety and tolerability of the antimicrobial PD catheter, defined as the rate of adverse events attributable to the antimicrobials or the impregnation process encountered by PD patients.

## 2.2. Secondary Objectives

Assessment of Patient acceptability PD Peritonitis Rates Exit site/tunnel infection rates Technique failure (transfer from PD to HD) Microorganism colonisation of PD catheters removed within the study period Antibiotic resistance profile of organisms causing catheter-related infections

## 2.3. Primary Endpoint/ Outcome

The rate of adverse events attributable to the antimicrobials or the impregnation process encountered by PD patients.

## 2.4. Secondary Endpoints/ Outcomes

Patient acceptability determined by modified IPOS Renal questionnaire and patient acceptability questionnaire

PD Peritonitis (identified and defined using local protocols and International Society for Peritoneal Dialysis Guidelines)

Exit site/tunnel infection (identified and defined using local protocols and International Society for Peritoneal Dialysis Guidelines)

Technique failure (transfer from PD to HD)

Microorganism colonisation of PD catheters removed within the study period Antibiotic resistance profile of organisms causing catheter-related infections

## 3. TRIAL DESIGN

Non-randomised feasibility study to gather preliminary information on the antimicrobial impregnated PD catheter to inform the design and the feasibility of conducting a randomised trial.

## 4. STUDY SETTING

This study will be undertaken at University Hospitals of Derby & Burton NHS Foundation Trust (UHDB) and participants will be recruited from patients already known under the care of the renal team at UHDB.

#### 5. ELIGIBILITY CRITERIA

All patients who opt for peritoneal dialysis (PD) will be invited to participate, subject to the following inclusion and exclusion criteria.

## 5.1. Inclusion Criteria

Aged 18 years or older End stage kidney disease (ESKD) of any cause Elective PD catheter insertion

#### 5.2. Exclusion Criteria

Documented allergy to rifampicin, sparfloxacin (or any fluoroquinolone), triclosan, or silicone Pregnant, likely to become pregnant, or breastfeeding Emergency PD catheter insertion

#### 6. TRIAL PROCEDURES

#### 6.1. Recruitment

#### 6.1.1. Patient Identification

Patients will be provided with information regarding the study once they have made a decision to have PD. This may be several months prior to starting dialysis. Once the decision is made to commence PD, patients will be asked whether they wish to participate and approached for consent to enter the study. They will be offered a date for PD catheter insertion, normally within 1-3 weeks.

#### 6.1.2. Screening

Patients are provided with extensive counselling in the months and weeks leading up to the need for renal replacement therapy and when choosing to have PD treatment and are provided with a separate patient information sheet relating to the insertion procedure and consent as part of routine care.

All patients who opt for PD at UHDB will be approached at a clinic visit by their clinical team and given information regarding the trial. For individuals already or previously on PD who are transferring back and require a new PD catheter they will be approached by the PD team.

There will be no payments to participants and no visits additional to routine care.

#### 6.2. Consent

Informed consent must be obtained prior to the participant undergoing procedures that are specifically for the purposes of the trial (including the collection of identifiable participant data, unless the trial has prior approval from the Confidentiality Advisory Group (CAG) and the REC.

The Principal Investigator (PI) retains overall responsibility for the informed consent of participants at their site and must ensure that any person delegated responsibility to participate in the informed consent process is duly authorised, trained and competent according to the REC approved CIP, principles of Good Clinical Practice (GCP) and Declaration of Helsinki.

Once individuals have been identified as eligible for inclusion they will be provided with a patient information sheet (PIS) and given time to consider the information. If they indicate that they are willing to participate they will then have a meeting with a member of the study team who will take consent for the study after answering any questions that they may have. Participants will still need to be consented separately by the clinical team for the PD catheter insertion procedure.

Only individuals who have capacity to consent are eligible to be recruited to this study. If they lose capacity at a later point they will continue within the study unless they have withdrawn consent prior to losing capacity. Any potential participant has the right to refuse participation without giving reasons

and this will not alter their care in any way. If required a trained interpreter will be provided. The PI takes responsibility for ensuring that all vulnerable subjects are protected and participate voluntarily in an environment free from coercion or undue influence.

If a participant wishes to withdraw from the study then no further data (aside from safety data) will be collected with regards to that individual. The PD catheter will remain in situ until such time as it is decided by the clinical team that it should be removed for clinical reasons.

## 6.3. Baseline Data

To be collected from the participants and medical notes

- Demographic information (Age, Sex, Height, Weight, Ethnicity)
- Previous renal replacement therapy (RRT), (modality, duration, complications)
- Past medical history (Angina, Previous MI, Previous CABG or coronary angioplasty, Heart disease, cerebrovascular disease, diabetes, chronic obstructive pulmonary disease, liver disease, malignancy, claudication, ischaemic/neuropathic ulcers, other (non-coronary) angioplasty, amputation for peripheral vascular disease
- Smoking history
- Current drug therapy and allergies
- Blood Results (enhanced set (see below))

#### 6.4. Trial Assessments

Outline of visit schedule; See Error! Reference source not found.

PD catheters at UHDB are inserted in interventional radiology (IR) with real-time x-ray screening (fluoroscopy) as standard care and the same will be the case for the research participants. Whenever there are concerns over the position of functioning of a PD catheter this is also assessed with a plain abdominal X-Ray. We do not anticipate any additional Radiation exposure as a result of this trial design or the use of the Antibiotic impregnated PD catheter.

PD catheter insertion counts as day 0 and will be undertaken in interventional radiology as per our standard of care for PD catheter insertions. A small number of PD catheters will require surgical insertion for patient related factors. For IR inserted catheters we have consulted a medical physics expert and IRMER (Ionising Radiation Medical Exposure Regulations) practitioner who have provided the following assessment.

#### Trial radiation procedures

A participant in this trial would undergo an insertion of a peritoneal dialysis catheter impregnated with antimicrobial treatment. Fluoroscopy imaging is used to guide the insertion. If there are concerns about catheter placement, a plain film abdominal x-ray may be carried out. The participant would have a catheter insertion whether in the trial or not, so the radiation in the study is consistent with standard care.

#### Estimated effective dose

Local dose audit for peritoneal dialysis catheter insertion resulted in a dose-area product of 0.2Gycm2 (n=39). Using conversion factor for abdominal examination from CRCE028 [1], this results in approximately 0.04mSv effective dose.

The NDRL for abdominal plain film x-ray is 2.5Gycm2 [2]. This results in approximately 0.45mSv effective dose [1].

#### Estimated risk

The estimated total research protocol dose is set at 0.5mSv. This is the equivalent of less than three months of UK background radiation. It would increase the individual's risk of cancer by 0.0025% (compared to our natural risk of cancer, of 50%) [1].

This exposure would take place as part of routine clinical care: participants taking part in this study will therefore not be exposed to any additional radiation through participation.

Details of assessments to be undertaken

- 1. Bloods tests:
  - a. All visits requiring bloods, electrolytes, urea, creatinine, calcium, phosphate, liver function tests, c reactive protein, full blood count,
  - b. Enhanced bloods as per routine care at 0, 3 and 6 months (ferritin, transferrin saturation, folic acid, vitamin B12, parathyroid hormone)
- 2. Exit site review: Exit sites will be examined by the PD nurse and a photograph will be taken and stored as part of the electronic patient record. This procedure is already a standard of care in the unit. Exit sites will be scored by the PD nurse and a PD consultant according to the scale developed by Schaefer et al Figure 5.

Exit-Site Scoring System			
		Score a	
Parameter	0	1	2
Swelling	No	Exit only	>0.5 cm
-		(<0.5 cm)	or tunnel or both
Crust	No	<0.5 cm	>0.5 cm
Redness	No	<0.5 cm	>0.5 cm
Pain	No	Slight	Severe
Drainage	No	Serous	Purulent

Exit-Site Scoring System

a Infection should be assumed with a score of 4 or higher. Purulent drainage, even by itself, is sufficient to indicate infection. A score of less than 4 may or may not represent infection.

Figure 5 Modified version of Schaefer F et al(14) as presented in the ISPD guidelines

3. Questionnaires:

IPOS Renal: To be completed at baseline, 3 weeks post PD catheter insertion and at 3 and 6 months post insertion (see Appendix 3 - IPOS Renal Questionnaire). IPOS Renal is a QOL measure for repeated measures in renal patients.

Acceptability questionnaire: to be completed at 3 months post catheter insertion.

Patient acceptability

How would you rate the tolerability of your PD catheter? (10 no problems, 1 intolerable)

How much do you value having antibiotics added to the catheter? (10 very much, 1 not at all)

Did you experience any specific problems related to the catheter? (Yes/No)

If yes, please describe any problems you experienced.

Any other comments about the catheter?

4. PD prescription details will be recorded and the reason for any change in prescription will be logged.

All blood and PD fluid tests will be part of routine care. All study visits will coincide with routine clinical visits. The IPOS Renal questionnaire is in addition to routine care. At 24 weeks after PD catheter insertion the study will be considered completed and individuals will continue with routine clinical care. Additional visits will be arranged if there are any concerns raised between routine visits.

Additional visits for foreseeable adverse events related to treatment with a PD catheter : See Figure 2, Figure 3, and Figure 4 for the flow diagrams of participant care leading to additional study visits

Any episode of PD related infection (exit site, tunnel or Peritonitis) will result in an extra visit and investigation/ treatment as per existing guidelines (Appendix 4 - PD Peritonitis Guideline). The results of these investigations and the clinical outcome will be recorded. If any microorganisms are isolated during the routine clinical processing of samples this isolate will be stored.

If a PD catheter is removed for any reason during the study period the catheter will be retained for further analysis by the study team.

All adverse events reported by participants will be recorded. Individuals transferring off PD will be recorded but individuals who stop PD due to a functioning kidney transplant or recovery of independent kidney function will not be recorded as adverse events.

In the event that a participant moves away for the area the receiving team will be informed of the fact that they are participating in a study and no further data will be collected. Due to the nature of the treatment and the relatively short duration of the study it is very unlikely that participants will otherwise be "lost to follow up" but every effort will be made to contact them and ensure appropriate follow up.

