## 6.5. Withdrawal Criteria

If a participant wishes to withdraw from the study then no further data (aside from safety data) will be collected with regards to that individual. The PD catheter will remain in situ until such time as it is decided by the clinical team that it should be removed for clinical reasons.

Participants will be withdrawn from the study if they have the PD catheter removed for any reason. The study may be stopped early if there is a concern about safety/tolerability of the novel PD catheter.

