#### 10.3.3. Secondary Outcome Analysis

Secondary outcomes will be analysed as follows:

- 1. IPOS Renal questionnaire: responses will be analysed using the methodology specified for this questionnaire. (see Appendix 5 IPOS AnalysisFor details
- 2. Patient acceptability questionnaire: scores will be summarised using descriptive statistics. Patient comments will be collated and used to inform future study design.
- 3. PD Peritonitis (identified and defined using local protocols and International Society for Peritoneal Dialysis Guidelines)
  - a. Rate will be calculated per patient year
  - b. Causative organisms will be reported and summarised using descriptive statistics.
- 4. Exit site/tunnel infection (identified and defined using local protocols and International Society for Peritoneal Dialysis Guidelines)
  - a. Rate will be calculated per patient year
  - b. Causative organisms will be reported and summarised using descriptive statistics.
- 5. Technique failure (transfer from PD to HD) rate will be reported per patient year
- 6. Microorganism colonisation of PD catheters removed organisms will be reported and summarised using descriptive statistics
- 7. Antibiotic resistance profile of organisms causing catheter-related infections will be reported and summarised using descriptive statistics

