## 10.6. Procedure(s) to Account for Missing or Spurious Data

Data will be collected using a case report form (CRF). Research nurses will be asked to complete all data fields and CRFs will be checked by the project manager upon completion. Missing data items will be obtained from the participants' clinical records. Research nurses will be asked to provide a reason for any data item that is missing.

We will not impute missing data.

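### The acceptability questionnaire has two conflicting schedules in the protocol, and neither asks for it at catheter removal, so the summary may favour acceptance

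*Protocol*

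**What the plan says.** Acceptability is a secondary endpoint with two instruments (Protocol 2.4): "Patient acceptability determined by modified IPOS Renal questionnaire and patient acceptability questionnaire".

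Section 6.4 times them differently. For the five-question acceptability form: "Acceptability questionnaire: to be completed at 3 months post catheter insertion". For IPOS Renal: "To be completed at baseline, 3 weeks post PD catheter insertion and at 3 and 6 months post insertion".

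Appendix 1 puts both instruments in one row, Assessment 1, ticked at Baseline and visits 9, 12 and 15. The column for additional visits, which covers infection episodes and removed catheters, is not ticked for that row.

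Section 6.5 states: "Participants will be withdrawn from the study if they have the PD catheter removed for any reason". For a participant who chooses to withdraw, the same section says "no further data (aside from safety data) will be collected with regards to that individual".

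On analysis, section 10.3.3 says "Patient acceptability questionnaire: scores will be summarised using descriptive statistics", and section 10.6 says "We will not impute missing data".

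**The concern.** There are two linked problems.

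First, site staff cannot tell from the protocol when to hand out the form. One passage gives a single time point and the other gives four, including one before the catheter is in place. The tolerability and problem questions cannot sensibly be answered then.

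Second, catheter removal ends participation, and no visible text asks for the form at that moment. People who lose the catheter early are plausibly among those with the worst experience of it. If they give no rating, the summary describes those who kept the catheter rather than those who received it.

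This matters because section 2 asks whether patients tolerate the catheter well and whether the data support later efficacy studies, and because patient comments are meant to inform future design (section 10.3.3). A SAP could set the denominator and the summary, but it cannot recover answers that were never collected.

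**Working it through.** **Plan's own figure.** The protocol attaches no number to acceptability. The only stated figure that early removal touches is the observation time in section 10.1: 40 × 6 = 240 patient months. It reproduces, but only if nobody leaves early.

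**The two schedules side by side.**
- Section 6.4: acceptability at 3 months; IPOS Renal at baseline, 3 weeks, 3 months and 6 months.
- Appendix 1: both at Baseline and visits 9, 12 and 15.
- Section 6.4 puts the enhanced bloods at 0, 3 and 6 months, and Appendix 1 ticks them at Baseline and visits 12 and 15. Visits 12 and 15 are therefore probably 3 and 6 months, and visit 9 probably 3 weeks. This is an inference; the table gives no dates.
- The four ticks match the IPOS Renal schedule exactly, so the acceptability questions may simply have been merged into the IPOS row.

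**Who has no planned rating.**
- Under section 6.4: anyone whose catheter is removed before 3 months.
- Under Appendix 1: anyone whose catheter is removed before visit 9 (a baseline answer is not a rating of the study catheter). Someone who loses it later has been asked at least once, but not at removal.

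**Is early loss plausible?** Section 8.2 gives a local peritonitis rate of about 0.37 per patient year. Over 3 months in 40 people that is 40 × 0.25 × 0.37 = 3.7 expected episodes. The Background section says peritonitis can lead to urgent removal. Not every episode does, and the protocol gives no removal rate.

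**Size, under assumptions.** Let k of 40 lose the catheter before being asked. Those asked average 8 of 10, and those not asked would have averaged s. All of k, 8 and s are assumed.

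Mean over all 40 = [(40 − k) × 8 + k × s] / 40, so the reported mean is too high by (k/40) × (8 − s).

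| k (share) | Asked | s = 8 | s = 5 | s = 3 | s = 1 |
|---|---|---|---|---|---|
| 2 (5%) | 38 | 0 | 0.15 | 0.25 | 0.35 |
| 4 (10%) | 36 | 0 | 0.30 | 0.50 | 0.70 |
| 6 (15%) | 34 | 0 | 0.45 | 0.75 | 1.05 |
| 8 (20%) | 32 | 0 | 0.60 | 1.00 | 1.40 |

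For example, with s = 3: k = 2 gives (38 × 8 + 2 × 3)/40 = 7.75, and k = 6 gives (34 × 8 + 6 × 3)/40 = 7.25, against a reported 8.0.

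For the Yes/No question on problems, assume 10% answer Yes among those asked and, as the extreme case, that everyone not asked had a problem. The figure for all 40 is (0.10 × (40 − k) + k)/40: 14.5% for k = 2, 19% for k = 4, 23.5% for k = 6 and 28% for k = 8.

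**The case against.** The strongest reply is that early intolerance would not go unseen. Adverse events and device deficiencies are recorded to 26 weeks (section 8.3), adverse events are the primary outcome, and technique failure is reported. IPOS Renal, the other acceptability instrument, is given at 3 weeks. The outcome is descriptive, in a single-arm feasibility study of 40, with no decision threshold tied to it. All of this stands and limits the consequence. It does not close the gap: event records are not the patient's own rating of the catheter, section 6.4 describes IPOS Renal as a quality-of-life measure, and it too has no time point at removal.

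A reader might infer more than the documents support:
- **That acceptability is asked only at 3 months, that early losers are never asked, and that months 4 to 6 are missed.** This holds only if section 6.4 prevails. Under Appendix 1 there is a form at visits 9 and 15 as well.
- **That the result is certainly biased.** Removal is for any reason, and section 6.4 itself recognises other endings: "individuals who stop PD due to a functioning kidney transplant or recovery of independent kidney function will not be recorded as adverse events". Those people need not be dissatisfied.
- **That all data collection stops at removal.** The sentence limiting further data is written for participants who wish to withdraw. Extending it to removal is reasonable but is an inference.

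The flow diagrams (Figures 1 to 4) were not legible in the text reviewed. Figure 4 concerns removal of a catheter that is no longer required, so it should be checked for a questionnaire step.

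**Conclusion.** The point holds as a scheduling contradiction with a collection gap. Section 6.4 and Appendix 1 disagree on when acceptability is asked, the baseline tick makes little sense for questions about experience of the catheter, and no legible text asks for the form at removal under either schedule.

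Under section 6.4 the summary may favour acceptance. The direction is likely, not certain. On the assumed inputs the shift in the mean runs from 0 to 1.40 points on the 1 to 10 scale, and from 0.25 to 0.75 for 2 to 6 early losses scoring 3 against 8. The mean moves modestly; the greater risk is that low scores and the comments behind them are absent altogether.

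It would be tempting to say that the reported share with low tolerability would be 0% when the truth is 5% to 15%. That follows only from giving every retained user a score of 8 and every early loser a score of 3. The protocol defines no low-tolerability threshold, so the claim should not be made.

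The protocol should be changed, because the analysis stage cannot repair it. Declining to impute is not itself an error for a descriptive outcome.

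**What to change.** 1. Reconcile section 6.4 with Appendix 1, giving IPOS Renal and the acceptability form separate rows.
2. Remove the acceptability questions from Baseline.
3. Give the five-item form at 3 months, at the existing 6-month visit, and at catheter removal or withdrawal if that comes earlier, where the participant agrees. Tick the additional-visit column accordingly, and state in section 6.5 that this one form may be collected at that point.
4. Report results by time point, with the number answering out of all who received the catheter, and show responses at removal separately with the reason for removal.

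The cost is a short paper form at contacts that already take place: slightly more participant burden and no extra visits. Ratings given around removal may be coloured by the event that led to it, which is why they should be shown separately rather than pooled with the scheduled ones.

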## 8.3. Recording and Reporting SAEs and USADEs

All AEs, SAEs and device deficiencies must be recorded from the time of written informed consent until 26 weeks after the insertion date.

All AEs and device deficiencies occurring during the duration of the study must be reported by the investigator within the CRF. The PI is responsible for checking for AEs and SADEs when participants attend for treatment and follow-up.

The following events are considered reportable:

- Any SAE (whether initially considered device related or not)
- Any device deficiency that might have led to a SAE if:
  - o Suitable action had not been taken or
  - o Intervention had not been made or
  - If circumstances had been less fortunate.
- New findings/updates in relation to already reported events

All reportable events must be recorded by the investigator using the Sponsor's SAE reporting form and emailed to UHDB within 3 calendar days of the research team becoming aware of the event; even if not all information is available at the time (further information should be provided on the Sponsor's SAE Follow Up Report Form). Any change of condition or other follow-up information should be sent to the Sponsor as soon as it is available, or at least within 3 working days of the information becoming available. Events will be followed up until the event has been resolved or a final outcome has been reached. Safety information will be reviewed during trial management group meetings.

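### Section 6.4 ends all data collection when a participant moves away, which conflicts with the requirement in section 8.3 to record adverse events to 26 weeks after insertion

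*Protocol*

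**What the plan says.** Three parts of the protocol bear on a participant whose follow-up at the trial site ends early.

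- **Moving away (section 6.4, Trial Assessments).** "the receiving team will be informed of the fact that they are participating in a study and no further data will be collected". No exception is made for safety data. The next sentence promises efforts to keep contact, but it concerns people who would otherwise be lost to follow-up, so movers are set apart from it.
- **Withdrawal (section 6.5, with the same rule in 6.2).** "If a participant wishes to withdraw from the study then no further data (aside from safety data) will be collected with regards to that individual". Section 6.5 adds: "Participants will be withdrawn from the study if they have the PD catheter removed for any reason".
- **Safety recording (section 8.3).** "All AEs, SAEs and device deficiencies must be recorded from the time of written informed consent until 26 weeks after the insertion date". On reportable events it adds: "Events will be followed up until the event has been resolved or a final outcome has been reached".

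The primary endpoint (section 2.3) is the rate of adverse events attributable to the antimicrobials or to the impregnation process. Section 10.3.2 reports adverse events by category and as a rate per participant observation month. Section 10.1 plans 240 patient-months of observation from 40 participants.

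**The concern.** A site that follows 6.4 stops recording safety events at the move. A site that follows 8.3 carries on to week 26. The protocol does not say which rule prevails. An event still open on the day of the move falls under opposite instructions: 6.4 closes the file, while 8.3 wants the event followed to its outcome.

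The ordering is also odd. Someone who withdraws keeps safety follow-up, while someone who still consents and has only changed address does not. Because 6.2 and 6.5 write the safety exception out in words, its absence from the similar sentence in 6.4 cannot safely be read as implied.

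At stake is safety information on a new implant in a small single-site study whose primary purpose is safety. Time lost to a move is always the later part of a participant's follow-up. The human exposure that section 1.1 cites for this formulation comes from a urinary catheter used for up to 84 days, so much of the lost time may lie beyond that experience.

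**Working it through.** **Comparing the rules**

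| Situation | Section | Safety data afterwards |
|---|---|---|
| Withdraws | 6.2, 6.5 | Kept |
| Moves away, consent intact | 6.4 | Stopped, no exception stated |
| Any participant, consent to week 26 | 8.3 | Required, no exception stated |

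Rows 2 and 3 cover the same person in the same period, so the conflict is direct. Row 1 covers a different person. Set against row 2 it shows an inconsistency between categories, but both of those rules can be followed.

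**Is the catheter still in place?** Section 6.4 does not say. Under 6.5, removal is itself a withdrawal, and nothing links a move to removal. A mover who is still in the study would therefore normally have the catheter in place. This is an inference from the text.

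**The plan's own figure (section 10.1).** 40 participants × 6 months = 240 patient-months, and 240 / 12 = 20 patient-years. This reproduces the stated total, which makes no allowance for movers.

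**Exposure lost.** The number of movers, *m*, is not in the protocol. Assume *m* = 1 to 3.

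Share lost = *m* × (6 − month of move) / 240

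| Movers (assumed) | Move at month 3 | Move at insertion (upper limit) |
|---|---|---|
| 1 | 3/240 = 1.25% | 6/240 = 2.5% |
| 2 | 6/240 = 2.5% | 12/240 = 5% |
| 3 | 9/240 = 3.75% | 18/240 = 7.5% |

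**Effect on the primary rate.** If observation months stop at the move, numerator and denominator stop together, and a move unrelated to device effects costs precision only. If months after the move were counted although no events were sought in them, then with a constant event rate and three movers at month 3 the rate would be multiplied by 231/240 = 0.9625, an understatement of 3.75%.

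**The case against.** Several points on the other side have force.

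- **Specific over general.** Section 6.4 could be meant as a carve-out from the general rule in 8.3. The protocol does not say so, and 8.3 names no exception, so the conflict remains.
- **Serious events may still arrive.** A reader might infer that device-related serious events after a move would never reach the sponsor. The text does not support that. Section 8.3 makes any serious adverse event reportable within 3 calendar days of the research team becoming aware of it, and the receiving team will know of the study. An event passed on would still be reportable. What stops is active collection.
- **Only one direct contradiction.** It is tempting to say that 6.4 also contradicts 6.2 and 6.5. Those sections govern withdrawal, not moving. They show that the 6.4 rule is out of line and supply ready wording for the repair.
- **Size.** The loss is a range on an assumed count. The upper limit needs every mover to leave at insertion. Movers also contribute events and time up to the move, so they are not lost from the group at risk.
- **Bias.** A rate per observation month, censored at the move, need not be biased, since moving house has no evident link to device effects.
- **Practicality.** This is a single-site study using a local paper case report form and local electronic results. Records from another unit may not be easy to obtain. This bears on how the data are collected; telephone contact with the participant is the easier route.

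**Conclusion.** The conflict between 6.4 and 8.3 is real and should be removed. Followed as written, 6.4 means that safety events are not actively sought after a move in a consenting participant who may still have the investigational catheter.

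The point is minor in size. With 1 to 3 movers at month 3 the loss is 3 to 9 of 240 patient-months (1.25% to 3.75%), with an upper limit of 2.5% to 7.5% for moves at insertion. The number and timing of movers are assumptions, since the protocol gives neither. The cost is mainly unrecorded safety events. The documents do not support a claim that the primary rate is biased, or that serious events after a move are certain to go unreported.

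**What to change.** Reconcile 6.4 with 8.3 by adding to the sentence on moving away the safety-data exception already used in 6.2 and 6.5. State that adverse events, serious adverse events and device deficiencies continue to be collected after a move, by telephone or through the receiving team, to the end of the 8.3 window unless consent is withdrawn. Outcomes that need a visit to the trial site can still end at the move.

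The cost is one sentence in the protocol and a few contacts, since the receiving team is already to be informed. It may also need a line in the consent wording on obtaining information from another unit, with an amendment under section 12.9.
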